Specific objectives:

1. To evaluate the effect of vitamin C, vitamin D and zinc supplementation on metabolic control (plasma glucose, HOMA, Hb1Ac and lipid profile).
2. To analyse the effect of vitamin C, vitamin D and zinc supplementation on inflammatory and immune biomarkers.
3. To analyse the effect of vitamin C, vitamin D and zinc supplementation on oxidative stress and antioxidant profile.
4. To evaluate the effect of vitamin C, vitamin D and zinc supplementation on gut microbiota.

4. Methods

Study design

Clinical trial randomized, prospective, placebo-controlled, double blinded, comparing two groups of patients with type 2 diabetes mellitus in the State of Mexico.

According to the calculation of the sample size, we will include 120 adults with type 2 diabetes mellitus selected from the outpatient preventive medicine offices of health centres in the State of Mexico who will be divided in two groups: supplement and placebo (60 per group). After having been invited to participate and obtaining the informed consent, study subjects will be evaluated for dietary information, as well as biochemical biomarkers of metabolic control, anthropometric, immune and inflammatory markers, gut microbiota and oxidative stress, before beginning the trial, and after 12 and 24 weeks of supplementation. They will have a monthly follow-up visit for evaluation of adherence and adverse effects, as well as delivery of the supplement.

Study groups

Subjects will be randomly allocated to a supplementation with 1000 mg vitamin C, 400 IU vitamin D and 10 mg of zinc or placebo group, during 24 weeks. Subjects and researchers will be blinded to the supplement or placebo in order to guarantee double-blinding.

Sample size calculations:

Based on a previous study done by this same research group (*Nutrients* 2017, 9, 573; doi:10.3390/nu9060573), we calculated the sample size with the data on the effect of a

6-month *n*-3 fatty acid supplementation trial on glucose concentrations of group of subjects with type 2 diabetes mellitus,

The calculations were done with the following formula:

$$N = \frac{(2 \times s^2)(Z\alpha + Z\beta)^2}{d^2}$$

Where: $Z_{\alpha/2} = 1.96$, $Z_{\beta} = 0.84$, $s = 68.9$ mg/dL and $d = 40$ mg/dL

Thus:

$$N = \frac{(2 \times 4747.21)(1.96 + 0.84)^2}{40^2} = 46 \approx 50 \text{ subjects}$$

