Accounting for a 20% loss at follow-up, we added 10 subjects, resulting in 60 subjects per group. This sample size guarantees that we should be able to observe significant differences in all the other indicators we will measure.

The following criteria will be used for the selection of the study sample:

Inclusion criteria

- Between 25 and 55 years of age, as this is the age in which type 2 diabetes mellitus is more prevalent and there is less probability of encountering multiple diseases in the same subjects
- Both sexes
- Outpatients
- BIM ≥ 25

Exclusion criteria

- Without any other chronic disease (cancer, cardiovascular diseases, arthritis and Alzheimer's).
- Severe renal insufficiency.
- Nephrolithiasis or history of nephrolithiasis.
- Hyperoxaluria.
- Hemochromatosis.
- Hypercalcaemia.
- Hypervitaminosis D.
- Using insulin.
- Be taking drugs such as desferrioxamine, iron, cyclosporine, indinavir (protease inhibitors), warfarin, thiazide diuretic, orlistat, ion exchange resins (e.g. cholestyramine, laxatives (e.g. mineral oil, senna), vitamin d analogues (e.g. ergocalciferol, calcitriol, and topical calcipotriene), tetracycline antibiotics, quinolone antibiotics, penicillamine, biphosphonates, levothyroxine, eltrombopag).
- Patients with hypersensitivity to any of the active substance(s) or to any of the excipients.
- Hypersensitivity to the by-products including honey, conifers, poplars, Peru balsam, and salicylate.

- Intake of probiotics or supplemental vitamin or mineral (vitamin D, C, zinc or calcium) for 4 weeks before the beginning of the study.
- Smoking and alcohol consumption (> 40 gr/ day for men and 25 gr/ day for women).
- Pregnant or lactating.
- Whose parents or grandparents are/were immigrant or of native origin.

Measurements.

Subjects will be selected from the outpatient preventive medicine offices of health centres in the State of Mexico. After having been invited to participate and obtaining their informed consent, study subjects will be evaluated for dietary information, as well as biochemical, anthropometric, immune and inflammatory markers, as well as intestinal microbiota before beginning the trial, at 12 and 24 weeks of supplementation.

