A qualified physician will do a complete clinical history. Subjects will be requested to fill-out the Diabetes 39 quality of life questionnaire (validated in Mexico), at baseline and at the end of the study. Questions on frequency of respiratory, urinary and gastrointestinal infections as well as on perception with respect to the supplement will be included.

A standardized nutritionist will evaluate Dietary History, a food-frequency questionnaire (FFQ), as well as three 24-hour food registry of non-consecutive days including one from the weekend. The FFQ will be analysed in DIAL software to evaluate dietary intake of vitamin C, vitamin D and zinc. Anthropometric evaluations will be done by a standardized nutritionist; weight will be measured with a 1631 TANITA™ portable electronic scale, stature with a 1013522 SECA™ portable stadiometer, for the calculation of BMI.

Faecal samples will be obtained for evaluation of intestinal microbiota. We will proceed to isolate and characterize the bacteria obtained from the faecal samples with two enriched culture media for the purification of the most representative and abundant strains. The isolated strains will be classified in morphological groups according to their macroscopic characteristics of size, form, surface, consistency and color. A selection of 40% of the representative samples from each morphologic group will be typified by the RFLP method. We will obtain biomass and extract DNA, for amplification of the 16S rRNA gene, with an enzymatic genotyping and strain grouping. The strains will be grouped to compare their diversity; the results of the groups will be compared to appreciate the differences between the type and number of strains obtained.

At each sampling date, a venous blood sample of 8.5 mL will be obtained after a 12 hour fast for the measurement of vitamin C (HPLC); zinc (Atomic Absorption Spectrometry); vitamin D and Vitamin D binding protein (ELISA); plasma glucose; triacylglycerides; total cholesterol; HDL and LDL-cholesterol and Hb1Ac (Automated Selectra equipment with Randox™ reactants); pro inflammatory cytokines (TNF α , IFN- γ , IL-1 β) and anti-inflammatory cytokines (IL4, IL-6, IL10, TGF- β), apolipoproteins A and B, C-reactive protein, V-CAM, I-CAM, complement proteins C-3 and C-4, insulin, adiponectin, resistin and leptin will be analysed with multiplex technology (Milliplex Luminex™). Additionally we will measure biomarkers of oxidative stress and

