A specific database will be designed in SPSS 19.0®. Data will be described with means and standard deviations or frequencies and percentages depending on the type of data. We will undertake a normality analysis, after which differences between groups will be analysed by parametric or non-parametric statistical tests. A multiple regression analysis will be run in order to establish interactions between variables.

References

Barengolts E. Vitamin D and prebiotics may benefit the intestinal microbacteria and improve glucose homeostasis in prediabetes and type 2 diabetes. *Endocr Pract* 2013; **19**(3): 497-510. doi: 10.4158/EP12263.RA.

Crook M. Type 2 diabetes mellitus: a disease of the innate immune system? An update. *Diabetic Medicine*. 2003; **21**:203-7.

Diabetes Public Health. From Data to Policy: Oxford University Press; 2011

Encuesta Nacional de Salud y Nutrición 2012. http://www.insp.mx/ensanut/resultados_ensanut.html.

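### The group comparison is picked by a normality check and does not commit to using baseline; a pre-specified baseline-adjusted comparison is likely to be more precise, at little cost

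*Combined protocol and SAP*

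**What the plan says.** The whole analysis plan is the short paragraph under Data Collection and Statistical Analysis at the end of the Methods. After descriptive statistics it says: "We will undertake a normality analysis, after which differences between groups will be analysed by parametric or non-parametric statistical tests". One more sentence follows: "A multiple regression analysis will be run in order to establish interactions between variables". Neither sentence names a test, a time point, final values or changes, or a baseline covariate. The stated aim of the regression is interactions; it names no outcome and no treatment term.

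Baseline data will exist. Under Study design, assessments take place "before beginning the trial, and after 12 and 24 weeks of supplementation". Under Measurements, the fasting blood sample is taken at each of these dates, and quality of life is collected with the "Diabetes 39 quality of life questionnaire (validated in Mexico), at baseline and at the end of the study".

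The sample size section uses plasma glucose, with s = 68.9 mg/dL and d = 40 mg/dL from the group's earlier n-3 fatty acid trial. It does not say whether s is the SD of final values or of change.

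**The concern.** Two things are left open that could be settled in advance.

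The first is precision. A participant's baseline value usually predicts the later value. A comparison that ignores it leaves explained variation in the error term, and a comparison of raw changes removes the wrong amount unless the slope on baseline is 1. Baseline adjustment costs one degree of freedom and needs no new data.

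The second is the effect measure. When the data choose between a parametric and a rank test, nobody knows beforehand whether a difference in means or a rank comparison will be reported, and the answer may differ across more than 30 markers. The trial is sized on a mean difference in mg/dL, which a rank test does not estimate.

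**Working it through.** **Inputs from the Sample size calculations section.** s = 68.9 mg/dL, d = 40 mg/dL, 1.96 (two-sided 5%), 0.84 (80% power). "Accounting for a 20% loss at follow-up, we added 10 subjects, resulting in 60 subjects per group".

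**The plan's own figure.** (2 × 4747.21)(1.96 + 0.84)² / 40² = 46.52 per group. The plan states 46, rounded up to 50, so it reproduces. Taking 20% off 60 leaves 60 × 0.8 = 48 evaluable per group, used below.

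**Assumptions that the documents do not supply.** Equal SD at baseline and week 24, and a baseline to week-24 correlation r, shown as a range.

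**Unadjusted test, run on the scale that s describes.** Standard error = 68.9 × √(2/48) = 14.06. Noncentrality = 40 / 14.06 = 2.84 on 94 df. Power is 80.4%. The 95% CI half-width is 1.986 × 14.06 = 27.9 mg/dL.

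**ANCOVA.** There are 93 df, and the variance is multiplied by 1 + 1/(2 × 48 − 4) = 1.0109 for chance baseline imbalance. The residual SD depends on what s is:
- s is the SD of final values: s√(1 − r²).
- s is the SD of change: a single value has SD s/√(2(1 − r)), so the residual SD is s√((1 + r)/2).

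Example at r = 0.5: residual SD = 68.9 × √0.75 = 59.7 on either reading. Standard error = 59.7 × √1.0109 × √(2/48) = 12.25, and half-width = 1.986 × 12.25 = 24.3.

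| r | Final-value reading: residual SD, power, half-width | Change reading: residual SD, power, half-width |
|---|---|---|
| 0 | 68.9, 79.9%, 28.1 | 48.7, 97.7%, 19.9 |
| 0.3 | 65.7, 83.5%, 26.8 | 55.5, 93.5%, 22.6 |
| 0.5 | 59.7, 89.8%, 24.3 | 59.7, 89.8%, 24.3 |
| 0.7 | 49.2, 97.5%, 20.1 | 63.5, 85.9%, 25.9 |
| 0.9 | 30.0, about 100%, 12.2 | 67.2, 81.9%, 27.4 |

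Each row compares with 80.4% and 27.9 unadjusted. Break-even is near r = 0.10 on the final-value reading, and the gain keeps growing above r = 0.7. On the change reading the gain is largest at low r, and break-even is near r = 0.98.

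**Skewed outcomes (simulation).** The data were log-normal, 48 per group, with an additive shift of 40/68.9 SD. No normality check is named, so the planned procedure was assumed to be Shapiro-Wilk at 5% in each group, then a t or Mann-Whitney test on final values. At skewness 0.95 and r = 0.3, power was about 85% for that procedure, 83% for untransformed ANCOVA and about 90% for log-scale ANCOVA. At skewness 1.75 and r = 0.3, untransformed ANCOVA had 83% against 93% for the assumed procedure, which at that skewness is almost always the rank test.

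**What the check does.** Type I error of the assumed procedure was 4.6% to 5.2% across normal and skewed data. At mild skewness (0.61) about half of the simulated trials went to each test, although the two tests agreed on significance in 94% to 95% of trials.

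**The case against.** The strongest reply is that parametric tests may include ANCOVA or a repeated-measures analysis, so the plan does not exclude baseline adjustment. That is true, and the computed loss therefore applies only if the test is run unadjusted. But nothing commits the investigators to adjustment, and pre-specification exists to close such choices.

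The size of the gain is also uncertain. It rests on r, which the documents do not give, and on an assumed equal SD. On the final-value reading it runs from a loss of 0.5 points (79.9% against 80.4%) to a gain of about 17 (97.5% against 80.4%) between r = 0 and r = 0.7. On skewed data the wrong scale can make ANCOVA worse than the planned approach. All of this stands, and it is why the scale must be part of the change.

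A reader might infer that choosing the test by a normality check makes the comparison invalid or inflates false positives. The documents do not support that: groups are randomised, and the simulated error rate stayed near 5%. Nor is the trial underpowered by its own standard, since the unadjusted test reaches about 80% on the scale that s describes. A reader might also infer that ANCOVA makes the meaning of s irrelevant. It does so only for the estimate, which is the same for final value or change. Power still differs, for example 97.5% against 85.9% at r = 0.7.

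**Conclusion.** The point holds as a cheap improvement and not as a flaw of validity. The plan selects its test from the data, leaves the effect measure open, and does not commit to using baseline values that it collects. For glucose, with 48 evaluable per group and r between 0.3 and 0.7, ANCOVA raises power from 80.4% to between 83.5% and 97.5% on the final-value reading, or between 85.9% and 93.5% on the change reading. These figures assume approximate normality, equal SDs and a true difference of 40 mg/dL. For skewed markers the benefit depends on naming a suitable scale in advance.

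**What to change.** Before unblinding, replace the normality-driven choice for continuous outcomes with a pre-specified ANCOVA of the week-24 value (study-end value for Diabetes 39), adjusted for the baseline value of the same variable. Report the adjusted group difference with its 95% CI. Name in advance which markers are log-transformed, for example from pooled blinded baseline values. State whether glucose is analysed in mg/dL, which keeps the scale used for sizing, or on the log scale, which gives a ratio. Keep a rank-based baseline-adjusted analysis as sensitivity. A mixed model that also uses week 12 is optional.

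The cost is a short addition to the analysis text and the work of settling scales for more than 30 markers; no new participants, visits or samples are needed. The downsides are one degree of freedom, ratio-scale effects for log-transformed markers, and possible loss of power against a rank test if a skewed, weakly correlated marker is left untransformed.

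### The plan expects 20% loss but names no time point, analysis set or missing-data method, so by default a week-24 glucose comparison would rest on completers alone; a baseline-adjusted model using both follow-up visits would be better and cheap.

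*Combined protocol and SAP*

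**What the plan says.** Under Study design, participants are assessed "before beginning the trial, and after 12 and 24 weeks of supplementation". The Measurements section includes plasma glucose in the fasting blood sample taken at each of those dates.

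The trial is sized on glucose, using data from an earlier six-month "supplementation trial on glucose concentrations of group of subjects with type 2 diabetes mellitus". The inputs are an SD of 68.9 mg/dL and a difference of 40 mg/dL. The only provision for loss is in the sample size: "Accounting for a 20% loss at follow-up, we added 10 subjects", giving 60 per arm.

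The whole analysis plan is the short section Data Collection and Statistical Analysis. After a normality check, "differences between groups will be analysed by parametric or non-parametric statistical tests". It then adds: "A multiple regression analysis will be run in order to establish interactions between variables". The documents do not name a test, a primary time point, an analysis set, a method for missing values or a repeated-measures model.

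**The concern.** An ordinary two-group test needs a value at the visit being compared. If nothing else is specified, a week-24 test omits everyone without a week-24 value. It also ignores the week-12 results of those who left after that visit, and everyone's baseline. The regression described is for interactions and does not fill the gap.

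Adding participants protects the number analysed, not the comparability of those who remain. Suppose poorly controlled participants tend to leave and the supplement has already lowered glucose by week 12. Then more of the poorly controlled leave the placebo arm, the remaining arms look more alike, and a real effect is understated. The sizing leaves little power to absorb this. A silent plan also lets the handling of missing values be chosen after the data are seen.

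**Working it through.** **The plan's own figure.** Inputs from Sample size calculations: z values 1.96 and 0.84, SD 68.9, difference 40.

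n = 2 × 4747.21 × (1.96 + 0.84)² / 40² = 46.5 per arm. The plan states 46 and rounds up to 50; 50 × 1.2 = 60. The figure reproduces.

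**Power after the expected loss, if loss is unrelated to glucose.** 60 × 0.80 = 48 per arm with a week-24 value. The standard error is 68.9 × √(2/48) = 14.06, and 40 / 14.06 = 2.84. Power is Φ(2.84 − 1.96), about 81% (80.4% by the t-test). The loss of numbers alone does no harm.

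**Precision gained from week-12 values.** With correlation ρ between weeks 12 and 24 and n₁₂ per arm having a week-12 value, the likelihood variance of the week-24 mean is s²[(1 − ρ²)/48 + ρ²/n₁₂]. If half of the 12 leavers per arm have a week-12 value, n₁₂ = 54. With ρ = 0.5, 0.75/48 + 0.25/54 = 0.02025, an effective n of 49.4 and power of 82.2%. Across ρ = 0.3 to 0.9 the effective n is 48.5 to 52.7. If every leaver has a week-12 value, power is 81.9% to 87.4%; if none has, the gain is zero. Correlation and timing of loss are assumptions.

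**Bias, by simulation.** Assumptions not in the documents: 60 per arm, normal glucose with SD 68.9, true week-24 difference 40 mg/dL, 20% overall loss all after week 12, visit correlations 0.5 to 0.8, log-odds of loss rising 1 to 2 per SD of week-12 glucose (odds ratios e¹ = 2.7 to e² = 7.4), same rule in both arms. At least 2,000 trials were simulated per scenario. Results for the unadjusted completers' test:

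| Effect present at week 12 | Mean estimate (mg/dL) | Power |
|---|---|---|
| Full (40) | about 32 to 37 | 68% to 75% |
| Half (20) | about 35 to 39 | 74% to 82% |
| None | about 40 (no bias) | above 80% |

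- The lowest values (32 mg/dL, 68%) need the full effect by week 12, correlation 0.8 and log-odds of 2. At log-odds of 0.5 with the full week-12 effect, the estimate is about 39 mg/dL and power 79%.
- With no effect at week 12, the week-12 distributions are the same in both arms. Loss then shifts both week-24 means equally and the difference is unaffected.
- With no treatment effect at all, the rejection rate stays near 5%.
- Completers adjusted for baseline average about 36 to 40 mg/dL. Power is 76% to over 99%. It stays above 80% when the three visits are equally correlated; the low end arises when correlation decays between visits.
- The likelihood estimate from all visits averages about 39 to 40.5 mg/dL.

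**A different mechanism.** If the 20% who leave one arm differ from that arm's completers by 10 to 40 mg/dL for reasons not mirrored in the other arm, the bias is 0.20 × 10 = 2 to 0.20 × 40 = 8 mg/dL, in either direction.

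**The case against.** The strongest objection is that silence is not a decision. A reader might infer that the plan has committed to a completers-only week-24 result and discards the week-12 data. The documents do not say that. No test or time point is named, imputation and repeated-measures tests are not excluded, and a separate week-12 comparison would use those values. This stands, and it is why the point is about what happens by default.

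A reader might also infer that a completers' test is valid only if loss is unrelated to glucose. That is too strong: with the same loss rule in both arms and no week-12 effect, it is unbiased even under strong dependence. Nor does this mechanism create false positives. Nothing in the documents supports odds ratios of 2.7 to 7.4 per SD, or a full effect by week 12.

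A third objection is that baseline adjustment alone does most of the work. For power this is correct. It removes only part of the bias, because baseline does not carry what week 12 shows about who leaves.

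Finally, placing all loss after week 12 favours the all-visit model. Participants lost earlier have no follow-up value, and the model does not help for them. This stands too; the documents give no timing.

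What survives is that a foreseeable 20% loss has no stated analysis, and a better one is available from data already planned.

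**Conclusion.** The concern holds as a modest weakness that is cheap to correct. By default, week-24 glucose would be compared in about 48 of 60 participants per arm, without baseline and without the week-12 values of late leavers.

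The size depends on assumptions outside the documents, above all on how much of the effect is present by week 12. Under the stated loss model, a 40 mg/dL effect shrinks by about 3 to 8 mg/dL if all of it is present (40 − 37 to 40 − 32), by about 1 to 5 mg/dL if half is (40 − 39 to 40 − 35), and not at all if none is. It would be wrong to conclude that the trial is underpowered through loss of numbers, or that its false-positive rate is raised by this mechanism.

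The all-visit model removes the bias that baseline adjustment leaves only as far as loss is explained by observed values.

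**What to change.** In Data Collection and Statistical Analysis, replace the sentence on between-group tests by:

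> Week-24 glucose is compared between the groups as randomised, using all participants with any post-baseline value, by a linear mixed model for repeated measures (weeks 12 and 24; group, visit, group-by-visit, baseline, baseline-by-visit; unstructured covariance). Other continuous markers are analysed in the same way, log-transformed if skewed. The number with no post-baseline value is reported by arm. In a sensitivity analysis, missing week-12 and week-24 values of all randomised participants are multiply imputed and the imputed week-24 values are shifted over a prespecified range by arm.

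The shift range should be written into the plan before unblinding; the documents give no basis for a figure. The sensitivity analysis also brings in participants lost before week 12, whom the main model leaves out.

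The cost is a few sentences and a little more programming; the MIXED procedure in SPSS, the package the plan names, fits the main model. No visit or sample is added. The downside is a missing-at-random assumption, which the sensitivity analysis probes.
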